Participants will be paid \$160 for completing the study. They will earn \$30 for completing Virtual Visit 1, \$15 per visit for completing Virtual Visits 2-5, \$20 for Virtual Visit 6, plus a \$50 bonus for completing the study. Participants who do not meet enrollment criteria at Virtual 1 will earn \$20 for attending the visit. Participants who start but do not complete the study will receive payments for the virtual visits attended. They will not receive the \$50 completion bonus. Participants will also be reimbursed up to \$20 per in-person lab visit for transportation costs.

ANALYSIS PLAN

Primary Outcome

- Number of cigarettes purchased (analyzed as raw data and using derived behavioral economic measures).

Secondary Outcomes

- E-liquid purchased (analyzed as raw data and using derived behavioral economic measures).
- Relative importance and utility data from discrete choice experiment
- Perceived Health Risk Scale scores
- Product Evaluation Scale scores
- Minnesota Nicotine Withdrawal Scale scores
- Questionnaire on Smoking Urges scores
- Tobacco Product Interest scores
- Tobacco Policy Questionnaire scores

Exploratory Outcomes

- Themes emerging from the qualitative interviews
- Product use during Field Assessment
- Biomarkers of exposure during Field Assessment

Sample Size/Estimation/Analysis

Statistical analysis plan

This ETM study will use a 2x2 factorial design. The primary objective will be to evaluate the effect of the two factors – e-liquid nicotine content (moderate vs. low) and e-liquid flavors (all flavors available vs. only tobacco flavor) – on purchasing behavior during virtual visits 2 – 5. Product use behavior, biomarkers of exposure, and other measures of smoking behavior during the field assessment will be evaluated in exploratory analyses.

Analysis of the Primary Outcome

The primary outcome will be the number of cigarettes purchased during the virtual visits. These data will be analyzed both in their raw form (i.e. the raw number of cigarettes purchased) and using derived behavioral economic measures. This is a within-subject design, with each participant providing data under all four factor combinations, and, for the raw data, each participant will provide data for all price combinations nested within a visit.

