While participating in the study, adverse events will be assessed at Virtual Visit 6 and carbon monoxide levels from In-Person Lab Visit 3. Adverse events will typically be identified during the administration of the Health Changes Questionnaire. Other adverse events may be identified by spontaneous reports from the participant. Withdrawal symptoms are considered an adverse event if the symptom had a significant impact on the participant's daily life, caused a major disruption of functioning, or took any medication for it.

- **Health Changes Questionnaire:** If the participant answers "YES" to Questions 1, 2, or 3 the interviewer should assess for adverse events.
 1. Have you had any negative changes in your physical or mental health since your last virtual visit? If yes, briefly describe.

2. Since your last virtual visit, have you received any form of medical care? If yes, briefly describe.
3. Have you had any changes in medication since your last visit?

Physiological data that will be reviewed:

1. CO level: The 'Adverse Event Form' will be completed if the average of two (or three) consecutive measurements in the same visit is:
 - o CO is greater than 50 ppm if CO at Screening/Baseline Visit is < 20 ppm.
 - o CO is greater than 60 ppm if CO at Screening/Baseline Visit is 20 – 34 ppm.
 - o CO is greater than 70 ppm if CO at Screening/Baseline Visit is 35 – 49 ppm.

For the participant's protection, participants will be withdrawn immediately from the study if any of the following occur:

1. Cardiovascular disease (CVD) event: Typically includes MI (heart attack), PTCA (angioplasty/stenting), bypass surgery, stroke, peripheral vascular disease (arterial blockages in arms or legs leading to procedure or surgery). Less common CVD problems would be new cardiac arrhythmias (e.g., new atrial fibrillation) or new valvular disease (e.g., mitral or aortic regurgitation).
2. DVT/PE (deep vein thrombosis/pulmonary embolism, i.e., blood clots in the venous system).
3. Suicide Attempt: A participant will be withdrawn if they attempt suicide at any time during participation in the study
4. Psychiatric Hospitalization: A participant will be withdrawn if they are hospitalized for psychiatric reasons at any time during participation in the study.

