5. Pregnancy: If a participant indicates they are pregnant at Virtual Visit 6 or In-Person Lab Visit 3, they will be withdrawn from the study, and this event will remain open until delivery. At that time the license medical monitor will contact the participant to ask a few questions about the baby's health and will update the open 'Adverse Event Form'.

The following will be monitored and can lead to the participant being withdrawn by the PI:

1. Expired breath CO >80 ppm
2. Any hospitalization or debilitation in which participation in the study could be detrimental to the recovery process. This will be self-reported by the participant and will be reviewed by the site PI and medical monitor to determine whether continued participation in the study is appropriate.
3. If a participant is behaving in an inappropriate or threatening manner, admits to lying about eligibility criteria, including omitting previous medical diagnoses and medications, is participating in other smoking research studies that could affect the primary outcome measures, does not follow study instructions, etc., then the PI can withdraw them from the study at the PI's discretion.
4. If a participant fails to attend her/his Virtual Visit 1 within the 21-day allowable visit window, they will not be eligible to reschedule the visit or continue participation in the study.

References

http://www.ncbi.nlm.nih.gov/entrez/query.fcgi?cmd=Retrieve&db=PubMed&dopt=Citation&list_uids=10465828
2. Kozlowski, L. T. (2015). Prospects for a nicotine-reduction strategy in the cigarette endgame: Alternative tobacco harm reduction scenarios. *International Journal of Drug Policy*, 26(6), 543-547. doi:10.1016/j.drugpo.2015.02.001
3. Kozlowski, L. T. (2016). Cigarette prohibition and the need for more prior testing of the WHO TobReg's global nicotine-reduction strategy. *Tobacco Control*. doi:10.1136/tobaccocontrol-2016-052995
4. Kozlowski, L. T. (2017). Let actual markets help assess the worth of optional very-low-nicotine cigarettes before deciding on mandatory regulations. *Addiction*, 112(1), 3-5. doi:10.1111/add.13515
5. Shatenstein S. Eliminating nicotine in cigarettes. *Tob Control* 1999;8(1):106; author reply 07-9
http://www.ncbi.nlm.nih.gov/entrez/query.fcgi?cmd=Retrieve&db=PubMed&dopt=Citation&list_uids=10465827

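### The $50 completion bonus has no stated exception for safety withdrawals, which gives participants a financial reason not to report events that the study learns of mainly from them

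*Combined protocol and SAP*

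**What the plan says.** **Payment.** Compensation states: "Participants will be paid \$160 for completing the study". The parts are $30 for Virtual Visit 1, $15 for each of Virtual Visits 2 to 5, $20 for Virtual Visit 6 and a $50 bonus. For those who stop early: "Participants who start but do not complete the study will receive payments for the virtual visits attended". The next sentence reads: "They will not receive the \$50 completion bonus". The section does not separate people who drop out from people the study removes, and it does not define completion. In-person visits carry only transport reimbursement of up to $20 each.

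**Withdrawal.** Identifying Adverse Events says that "participants will be withdrawn immediately from the study if any of the following occur". The list is a cardiovascular event, DVT/PE, a suicide attempt, psychiatric hospitalization and pregnancy. On pregnancy: "If a participant indicates they are pregnant at Virtual Visit 6 or In-Person Lab Visit 3, they will be withdrawn from the study". A second list gives grounds on which the PI may withdraw a participant. It includes other hospitalization or debilitation where staying in could harm recovery.

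**How events become known.** "Adverse events will typically be identified during the administration of the Health Changes Questionnaire". Virtual Visit 6 lists that questionnaire among the self-administered surveys. Spontaneous reports are the other stated source. For hospitalization under the discretionary list: "This will be self-reported by the participant and will be reviewed by the site PI and medical monitor". A urine pregnancy test is described at In-Person Lab Visit 1 (Avoiding Risks during Pregnancy calls it the Screening Visit) and at no later visit.

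**The concern.** Read together, these rules link a participant's pay to her own account of her health. If she reports an event on the mandatory list, she is withdrawn. Under the general rule she is then a non-completer and loses the bonus. If she says nothing, she keeps it. For most of these events the protocol describes no independent check.

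What is at stake is the completeness of safety data. Some qualifying events might go unreported. A pregnancy that is not disclosed would not enter the follow-up to delivery that the protocol provides for. An event before In-Person Lab Visit 2 that is not disclosed could leave a participant in the seven-day product-use period although the protocol calls for withdrawal. Product adherence stresses honest self-reporting of product use, but the safety section has no comparable protection.

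**Working it through.** **1. The plan's total.** Inputs are from Compensation.

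30 + 4 × 15 + 20 + 50 = 160. This reproduces the stated $160 exactly.

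**2. Size of the bonus.** 50 / 160 = 31.25% of total pay. Visit pay alone is 160 − 50 = $110, and 50 / 110 = 45%.

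**3. Pay lost by the point of withdrawal.** Loss = 160 − visit pay earned so far. The last column restores the bonus only.

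| Withdrawn after | Paid | Lost | Share of $160 | Lost if bonus kept |
|---|---|---|---|---|
| Virtual Visit 1 | $30 | $130 | 81% | $80 |
| Virtual Visit 2 | $45 | $115 | 72% | $65 |
| Virtual Visit 3 | $60 | $100 | 63% | $50 |
| Virtual Visit 4 | $75 | $85 | 53% | $35 |
| Virtual Visit 5 | $90 | $70 | 44% | $20 |
| Virtual Visit 6 | $110 | $50 | 31% | $0 |

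Virtual Visit 6 is the one visit with a planned adverse-event questionnaire. From then on, the bonus is the whole of the payment at stake, because In-Person Lab Visit 3 is not itself paid.

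**4. Who supplies the information.**

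| Event | Withdrawal | Source after In-Person Lab Visit 1 |
|---|---|---|
| Cardiovascular event, DVT/PE, suicide attempt, psychiatric hospitalization | Mandatory | Questionnaire or spontaneous report |
| Pregnancy | Mandatory | Participant says so; no repeat test described |
| Other hospitalization or debilitation | PI's discretion | Self-report, then review |
| Expired CO above 80 ppm | PI's discretion | Measured |

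The disincentive applies to the first three rows. It does not apply to CO, which is measured and cannot be withheld. CO in turn detects none of the other events.

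**5. Cost of keeping the bonus.** The documents give no rate of safety withdrawal, so a range of 1% to 10% is assumed.

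- 100 recruited (the planned maximum): 50 × 100 × 0.01 = $50, to 50 × 100 × 0.10 = $500.
- 64 participants: 50 × 64 × 0.01 = $32, to 50 × 64 × 0.10 = $320.

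**The case against.** A reader might infer that the plan pays people to conceal events, or that adverse events and pregnancies will be under-counted. The documents support neither as fact. They contain no evidence of intent, of concealment or of its frequency. The incentive also works only if participants know that a truthful answer leads to withdrawal and loss of the bonus, and nothing visible says that they are told this. Most adverse events do not lead to withdrawal at all: a positive answer on the questionnaire only prompts the interviewer to look further.

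Other points on this side are also fair.

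- Loss of the bonus on safety withdrawal is inferred from the general rule, which does not mention safety withdrawals. A participant withdrawn at In-Person Lab Visit 3, with every paid visit done, might be treated as a completer.
- The consent pages are not in this file and could contain an exception.
- Only psychiatric hospitalization requires withdrawal. Other hospitalization is reviewed case by case.
- A serious event may itself prevent attendance, so the bonus could be lost whatever the participant says.
- Exposure is short. From In-Person Lab Visit 1 to In-Person Lab Visit 3 is about 1 + 3 + 0 + 7 + 0 = 11 days on the ideal schedule and at most about 21 + 3 × 7 + 2 + 7 + 2 = 53 days. The eligibility criteria exclude serious medical or psychiatric conditions and intended pregnancy, so few events are likely.
- Silence at Virtual Visit 6 does not prolong the seven-day field assessment, which is already over.

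These points limit the size of the problem and the strength of the wording. They do not remove it. The rule as written makes no exception, the events depend on self-report, and disclosure can cost money. If the sponsor already regards safety withdrawals as completers, Compensation should say so.

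**Conclusion.** The point holds as a disincentive in the payment rule. It is not a finding that events are concealed. Under the rule as written, disclosing an event that leads to withdrawal costs the $50 bonus, 31% of total pay, plus pay for any visits not yet attended. This may reduce the completeness of safety reporting and of pregnancy follow-up, by an amount the documents do not allow anyone to estimate.

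The conclusion rests on two readings: that a participant withdrawn by the study counts as a non-completer, and that the consent form makes no exception. The payment rule does not change the primary analysis or the power calculation. The change is worth making because it is cheap and bears directly on safety reporting.

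**What to change.** Add a sentence to Compensation: participants withdrawn by the study for an event on the mandatory withdrawal list, or for a self-reported hospitalization, still receive the $50 completion bonus. Put the same statement in the consent form if it is not already there. CO-based withdrawals are left out, because the rationale covers only events that depend on the participant's report. The withdrawal rules stay as they are, and nothing changes for voluntary dropout or withdrawal for conduct.

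The fix is partial. Pay for visits not attended is still lost, so disclosure becomes fully payment-neutral only from Virtual Visit 6 onward. After Virtual Visit 5, for example, the loss falls from $70 to $20.

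The cost is the wording change plus $50 per safety withdrawal, in total $50 to $500 under the assumed 1% to 10% of 100 participants. There is also a small risk that someone reports a false event to collect the bonus early.

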Discrete Choice. Interdisciplinary research describes choice as a function of the relative expected value of the options at hand.^{61, 62} Further, an option’s anticipated value is derived from the integrated values of its individual attributes.^{63, 64} Widely used in consumer research, discrete choice experiments (DCEs) reveal the extent to which individual product attributes determine choice.⁶⁵ In DCEs, across several trials, participants chose their preferred option from a selection of products, each described as a set of attributes. The products/combinations of attributes presented in each trial are experimentally varied such that the relative importance of each attribute can be discerned using logistic regression. In tobacco regulatory science DCEs have been used

frequently to evaluate general preferences for cigarette and vaping device characteristics.⁶⁶⁻⁶⁹ Here, we will use the DCE method to investigate the contribution of nicotine content and flavor availability to choices between cigarettes and vaping devices.

OBJECTIVES

We are proposing a four condition ETM study to determine if banning NNC is sufficient for encouraging smokers to switch to potentially less harmful products or if the availability of higher nicotine and/or flavored alternative products (specifically e-cigarettes) are needed to achieve maximal reductions in smoking.

METHODS AND MEASURES

Overall Study Design

We propose to conduct a within-subjects, multi-session virtual lab study and validation field assessment to determine how the availability of flavored e-liquids affects product purchasing among cigarette smokers. Adult daily cigarette smokers (N=64) will be recruited for this study. After initial eligibility is assessed, participants will complete six virtual sessions (1 baseline, 4 experimental, and 1 follow-up) and three in person sessions with one field assessment to evaluate their tobacco use.

Design and Setting

Participants will be recruited from Winston-Salem, NC and the surrounding area using advertisements on public transit, community flyers, and social media.. In-person lab visits to drop off biosamples and pickup study products will be conducted at the Wake Forest Tobacco Control Center of Excellence located in Biotech Place in the Innovation Quarter.

Subject Selection Criteria

We anticipate recruiting up to 100 participants to achieve 64 completers.

Inclusion criteria:

1. 21+ years of age

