Discrete choice task 1: The Sawtooth Lighthouse Studio platform will host a discrete choice task (See DCE Questionnaire). First, participants will rate the appeal of cigarettes and e-cigarettes characteristics, which helps familiarize them with the product features that will be manipulated in the choice task. Next, the choice task will begin, and they will make several choices between a cigarette option and an e-cigarette option responding to a prompt that asks which they would rather use exclusively for the next week. Each cigarette vs e-cigarette trial will present different combinations of cigarette nicotine content, e-liquid nicotine content, and e-liquid flavor. Finally, the participant will complete follow-up questions about which characteristics most informed their choices. The data from this task will reveal how participants prioritize and make tradeoffs between product type, nicotine content, and flavor when forming preferences.

After completing the discrete choice procedure, participants will also be given the opportunity to sample the low and normal nicotine Spectrum investigational cigarettes available during the ETM (up to 4 puffs each). Other products will also be available on the ETM, but will not be available for sampling. These include: fruit, dessert, menthol, and tobacco flavored e-liquids; and mint, fruit and cinnamon flavored nicotine gum.

Virtual Visits 2-5

Participants will complete Virtual Visit 2 between 1 and 21 days after completing In-Person Lab Visit 1. Virtual Visits 2-5 will ideally be conducted four days in a row to reduce online task fatigue. However, visits may be scheduled up to 7 days apart.

The following assessment will be administered as an interview and entered into REDCap by the interviewer:

1. Timeline Follow Back (TLFB) Questionnaire, which will assess tobacco and nicotine product use since their last virtual visit.

Participants will complete the ETM task on the computer. If the participant needs assistance with navigating the online marketplace the research staff may screen share and allow the participant to verbally select the items that they would like to purchase. The products available on the ETM include:

- Spectrum cigarettes
- Fruit, dessert, mint and tobacco e-liquids (e.g., Vaporesso Xross Mini)
- Mint, fruit, and cinnamon nicotine gum (e.g., Nicorette).

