Participants will undergo one of four marketplace conditions during Virtual Visits 2-5, with the order of administration randomized across participants.

- Marketplace Condition 1 includes moderate nicotine content vape with all flavor e-liquids.
- Marketplace Condition 2 includes moderate nicotine content vape with tobacco e-liquids.
- Marketplace Condition 3 includes low nicotine content vape with all flavor e-liquids.
- Marketplace Condition 4 includes low nicotine content vape with tobacco e-liquids.

Staff will instruct participants to complete the ETM task as if they are purchasing the products from a retailer, and that one iteration of the task will be randomly selected and will determine which products they will use during the field assessment. In reality, we will randomly assign which condition is used (Condition 2 or 4) but will assign products based on when NNC were not available to simulate a nicotine content reduction policy.

For each marketplace condition, participants will complete 7 iterations of the ETM task in ascending order. The prices for NNC cigarettes on the ETM will be set at: \$0.12, \$0.25, \$0.50, \$1.00, \$2.00 per cigarette; in the 1st ETM condition, NNC cigarettes will be set at \$0.25 with no VLNC available to purchase to simulate current market status; while in the 6th ETM condition, NNC will be eliminated from the marketplace to simulate a nicotine content reduction policy. The costs for the other products will reflect average prices in NC and will not change during the task. For each task iteration, participants will receive individually-tailored account balances approximately equal to the money they would spend on cigarettes for seven days. They can purchase as many or few products as their account balance allows. Participants are not required to buy products from the ETM or can buy nicotine gum if they prefer. If they do not buy products from the ETM and do not use tobacco products during the field assessment, then they will receive their ETM account balance at Virtual Visit 6. This payment is delayed to reduce the likelihood that they will use this money to buy their preferred brand cigarettes, thus decreasing the validity of the ETM task.

Participants will be instructed to use only the products purchased from the ETM during the subsequent 7-day period after Virtual Visit 5 and told that we will assess adherence at Lab Visit 3.

In-Person Lab Visit 2

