In-Person Lab Visit 2 will be completed up to 48 hours after completing Virtual Visit 5. Participants will complete the COVID screener within 24 hours of their Lab visit via email or phone. Research staff will wear personal protective equipment during the visit including face masks and gloves. The participants will be required to wear facemasks when interacting with the staff. Temperature checks will be conducted immediately upon arrival using a thermal heat scanner.

Participants will provide CO readings be at least 6-feet away from other people, including the research staff, while they have their masks off.

Participants will be given the products they purchased during the ETM task and will be instructed to only use these products for the next seven days. They will also be given a urine collection cup and instructions for sample collection.

The field assessment validates the ETM task by having participants use the products in the real world, simulating the different regulatory environments. Actual product use enables us to measure their subjective experiences such as withdrawal, craving, or product satisfaction as well as assess changes in carbon monoxide exposure, a biomarker of harm, when using products other than menthol cigarettes. We will conduct between-subjects analyses comparing these secondary outcomes by marketplace condition.

Virtual Visit 6

Participants will complete Virtual Session 6 seven days after completing In-Person Lab Visit 2.

The following baseline assessments will be administered as an interview and entered into REDCap by the interviewer:

1. Timeline Follow Back (TLFB) Questionnaire which will assess past tobacco and nicotine product use since Virtual Visit 5.

The following surveys will be self-administered using REDCap:

1. Tobacco Policy Questionnaire
2. Minnesota Nicotine Withdrawal Scale
3. Questionnaire of Smoking Urges-Brief – Usual Brand Cigarette
4. Product Evaluation Scale – VLNC, E-Cigarette, Gum (whichever product(s) they select)
5. Perceived Health Risks Scale
6. Tobacco Product Interest Scale
7. Health Changes Questionnaire

Participants will complete the ETM task under the same marketplace condition from which they received their field assessment products. Exploratory pre-post field assessment analyses will examine how actual use of the products affects subsequent purchasing of those products.

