Raw data will be analyzed using a linear mixed-effects model that includes main effects for e-liquid nicotine content (low vs. moderate), e-liquid flavors (all vs. tobacco only), visit, price condition (analyzed as a categorical variable), and a carryover effect for the previous visits condition (treated as a four-level categorical variable, and random effects for participant and visit nested within participant. This will account for correlation from multiple observations from the same participant, both within and across visits. We will also evaluate whether there is an interaction between the e-liquid nicotine content and e-liquid flavors factors. If significant, the interaction will be included in the model; otherwise, it will be removed. The analysis of derived behavioral economic measures will follow an analogous approach, except that for each measure, there will only be a single outcome for visit. As a result, our linear mixed-effects model will not include a main effect for price condition, and there will only be a single random effect for each participant. Behavioral economic measures will be derived by generating demand curves using an exponential demand equation. Specific measures considered will include: Alpha - the rate of change in demand, and Q_0 – peak consumption. For all analyses, assessments of key model assumptions will be completed and we will consider transformations or alternate analytic approaches if these assumptions are violated.

Analysis of Secondary Outcomes

The analysis of secondary endpoints will be analogous to the analysis described above for the primary endpoints. The amount of e-liquid purchased will be analyzed both as the raw data for each price condition and using derived behavioral economic measures. The analysis of these endpoints will be completed using linear mixed-effects models with the fixed and random effects terms described above. The analysis of the various scales and scores collected at each visit will follow the same approach as the analysis of derived behavioral economic measures described above. As before, assessments of key model assumptions will be completed and we will consider transformations or alternate analytic approaches if these assumptions are violated.

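### The purchasing models have no factor-by-price-condition term, so the flavor and nicotine effects are never estimated in the iteration where normal-nicotine cigarettes are removed

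*Combined protocol and SAP*

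**What the plan says.** The Objectives section sets a two-part question. The first part is to "determine if banning NNC is sufficient for encouraging smokers to switch to potentially less harmful products". The second part asks, as the alternative, "if the availability of higher nicotine and/or flavored alternative products (specifically e-cigarettes) are needed to achieve maximal reductions in smoking".

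Under Virtual Visits 2-5, participants complete seven iterations of the Experimental Tobacco Marketplace (ETM) task in each of four marketplace conditions (e-liquid nicotine by flavor). In one iteration, "NNC will be eliminated from the marketplace to simulate a nicotine content reduction policy"; I call this the ban iteration. Each participant therefore supplies it under all four factor combinations.

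The raw-data model under Analysis of the Primary Outcome "includes main effects for e-liquid nicotine content (low vs. moderate), e-liquid flavors (all vs. tobacco only), visit, price condition (analyzed as a categorical variable"), with a carryover term and random effects for participant and for visit within participant. A nicotine-by-flavor interaction is tested and dropped if not significant. No other interaction is named. Under Analysis of Secondary Outcomes, e-liquid is analyzed as raw data by price condition, but the section then applies the same fixed and random terms.

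For the field assessment, Virtual Visits 2-5 says "we will randomly assign which condition is used (Condition 2 or 4") and that staff "will assign products based on when NNC were not available to simulate a nicotine content reduction policy". In-Person Lab Visit 2 adds: "We will conduct between-subjects analyses comparing these secondary outcomes by marketplace condition".

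**The concern.** The Objectives question concerns the effects of flavor and nicotine once NNC are gone. A model without factor-by-price-condition terms forces each factor to have one effect across all iterations, whether NNC cost \$0.12, cost \$2.00 or are not sold.

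The protocol's own rationale makes a constant effect doubtful. The background argues that nicotine and flavor may matter because they help e-cigarettes compete with very low nicotine content (VLNC) cigarettes. That suggests an effect that depends on which cigarettes are on sale.

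If the factors matter more after the ban, the average understates their effect there. If they matter mainly while NNC are available, it overstates it. If the effect is constant, averaging is correct and more precise. The plan has no purchasing estimate that shows which case applies in the ban iteration, and the average could be reported as the policy answer.

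**Working it through.** **1. Does another planned analysis fill the gap?**

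- *Alpha and Q0* come from a demand curve over price and give one value per visit. A factor effect on alpha reflects differences over the priced iterations. The ban iteration has no NNC price and does not enter.
- *Cross-price elasticity* is a slope on log cigarette price, so the same limit applies.
- *Field assessment*: Conditions 2 and 4 both offer tobacco flavor only. They give an exploratory, between-participant nicotine contrast in product use under the ban, and no flavor contrast. With an assumed 32 versus 32 of the 64 completers, a two-sample t-test has 80% power for about 0.71 SD (0.65, 0.57 or 0.43 SD after adjusting for a baseline correlated 0.4, 0.6 or 0.8 with the outcome).
- *Pre/post paired t-tests* compare time points, not factor levels.
- *Discrete choice task*: stated preference, with no interaction with cigarette nicotine content specified.

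None gives a factor contrast on purchasing in the ban iteration.

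**2. The plan's own power figure.** The Power calculation gives 80% power for a main effect of 0.45 at within-participant correlation 0.4. A closed form with one observation per visit and two-sided 5% (assumed) gives (1.960 + 0.842) × √((1 − 0.4)/64) = 0.27. The simulation settings are not in the text and the figure is not available, so I do not call this an error. The point here does not depend on it, and no power is given for the ban iteration.

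**3. What the averaged coefficient estimates.** Inputs: seven iterations, read as current market, five NNC prices and NNC eliminated. Assumptions: all seven enter the model, data are complete, and the count includes VLNC cigarettes. Let D be the ban effect and rD the mean effect in the other six. The coefficient is (D + 6rD)/7 = D(1 + 6r)/7.

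| r | 0 | 0.25 | 0.5 | 1 | 2 |
|---|---|---|---|---|---|
| coefficient / ban effect | 14% | 36% | 57% | 100% | 186% |

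This needs no variance assumption. As an illustration, simulated data with a flavor effect of −7 cigarettes in the ban iteration only gave about −1.1 from the additive model (expected −7/7 = −1.0), against about −6.9 for that iteration from a model with factor-by-iteration terms.

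**4. Power (illustration only).** Let q = visit variance / residual variance of the other six iterations, and k = ban residual variance / that residual variance. The averaged contrast has variance proportional to q + (6 + k)/49, and the ban contrast to q + k. Their standard-error ratio is R = √[(q + k)/(q + (6 + k)/49)]. For an effect sized to give 80% power in the ban iteration, the averaged test has noncentrality w × R × (1.960 + 0.842), where w = 1/7 (ban only), 4/7 (half the effect elsewhere), 1 (constant) or 6/7 (everywhere except the ban).

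For example, at k = 1 and q = 0.25, R = √(1.25/0.3929) = 1.784. Ban-only noncentrality is 1.784 × 2.802/7 = 0.714, which gives 11.0% power.

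| k = 1 | q = 0.25 | q = 1 | q = 4 |
|---|---|---|---|
| R | 1.784 | 1.323 | 1.099 |
| Ban only | 11.0% | 8.3% | 7.2% |
| Half elsewhere | 81.5% | 56.3% | 42.0% |
| Constant | 99.9% | 96.0% | 86.8% |
| All but ban | 99.0% | 88.8% | 75.1% |

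Over k = 0.5 to 2 the four scenarios span 7–15%, 39–96%, 83 to >99.9% and 71 to >99.9%. Simulation at k = 1 with 64 participants, balanced orders, and visit and carryover terms agreed: ban only 10.7/9.3/6.9%, half elsewhere 81.2/57.8/41.2%, all but ban 98.6/88.3/75.7%.

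**5. Unequal residual variance.** If one residual variance is pooled across iterations, the nominal 5% error for the ban contrast becomes 1.4/2.6/4.0% at k = 0.5 and 12.3/9.8/7.0% at k = 2 (q = 0.25/1/4). Fitting the ban records alone gave 4.3–5.4% in simulation.

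**The case against.** The strongest reply is that the Statistical analysis plan defines the primary objective as the effect of the two factors on purchasing over Virtual Visits 2-5, without singling out an iteration. The Power calculation is for those effects, and the model estimates them. With the ban iteration as a level of price condition, it also gives the average effect of the ban itself. This stands: the primary analysis is valid for that objective. The gap is against the Objectives section.

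Second, the additive model does imply a factor effect in the ban iteration. It does so only by assuming it equals the effect elsewhere, which is not a separate estimate.

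Third, the plan promises checks of key assumptions and alternative approaches if they fail. Additivity could count, but no factor-by-price check is named, and such a response would be chosen after seeing the data. A transformation might make effects more nearly constant. The (1 + 6r)/7 relation still holds on whatever scale is modelled, although r depends on that scale.

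Fourth, the e-liquid wording could be read as separate analyses by price condition. The sentence after it reuses a price term and a visit-within-participant random effect, which do not suit a single-iteration model. At most this is an ambiguity for a secondary outcome.

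Fifth, the protocol does not state that the ban iteration enters the raw model. If it is left out, its weight is zero and the gap is wider. The variance ratios in the power table are also assumed, so that table shows direction and rough scale only.

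**Conclusion.** The concern holds and should be fixed. As written, no planned analysis of marketplace purchasing separately estimates the flavor or nicotine effect with NNC removed, or tests whether it differs from the effect elsewhere. This is firm for cigarettes and the better reading for e-liquid.

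The averaged coefficient would be 14% of the ban effect if the effect exists only under the ban, 57% if the other iterations show half of it, and 186% if they show twice as much. With equal residual variance and q from 0.25 to 4, the averaged test has 7–11% power in the ban-only case, and is significant 75–99% of the time when the effect is present everywhere except under the ban. If the effect is constant, nothing is lost. The percentages of the ban effect rest on seven roughly equally weighted iterations, all in the model, with VLNC cigarettes counted; the power ranges also rest on the assumed variance ratios.

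**What to change.** 1. Keep the averaged main effects for the objective in the Statistical analysis plan.
2. Code price condition as seven levels: current market, five NNC prices, NNC eliminated. State that the cigarette count includes VLNC (In-Person Lab Visit 1 describes "low and normal nicotine Spectrum investigational cigarettes available during the ETM"); otherwise the ban iteration is zero by construction.
3. Add nicotine-by-price-condition and flavor-by-price-condition terms to the cigarette and e-liquid models.
4. Pre-specify the flavor and nicotine contrasts within the ban iteration, for cigarettes and for e-liquid, as the estimates that answer the Objectives question. They can be key supportive contrasts. If the sponsor makes them confirmatory, adjust across the two, for example with Holm.
5. Let residual variance differ by iteration, or refit the ban records alone (one record per visit, participant random effect) as a check.
6. Reconcile the field-assessment passages. Virtual Visits 2-5 limits the field conditions to two with the same flavor setting, while Analysis of Exploratory Outcomes models both factors and their interaction.

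The cost is SAP wording and model terms, with no new visits or data. The ban-iteration interval is about 1.1 to 1.8 times as wide as that for the average at equal residual variance, and 1.04 to 2.33 times if that iteration's residual variance is half to twice that of the others. Adjusting across two contrasts, if chosen, raises the detectable effect by about 10%: (2.241 + 0.842)/(1.960 + 0.842) = 1.10.
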